#### 5.6.1.3 Study Drug Dose Reductions and Interruptions

Reasons for dose reduction and interruption, time to the first dose reduction and time to the first dose interruption for lenvatinib, everolimus and sunitinib will be summarized. Dose reduction refers to the situation that a dose level was reduced from the previous dose level without going back.

In the combination of lenvatinib plus everolimus treatment arm, the starting dose of lenvatinib is 18 mg/day. Lenvatinib dose reductions occur in succession based on the previous dose level (14, 10, and 8 mg/day). The starting dose of everolimus is 5 mg every day. Everolimus dose may reduce to 5 mg every other day until everolimus discontinue. In the combination of lenvatinib plus pembrolizumab treatment arm, the starting dose of lenvatinib is 20 mg/day. Lenvatinib dose reductions occur in succession based on the previous dose level (14, 10, and 8 mg/day and so forth). The starting dose of pembrolizumab is 200 mg per administration. Pembrolizumab must be withheld/interrupted or discontinued for drug related toxicities and severe or life-threatening AEs. In sunitinib treatment arm, the starting dose of sunitinib is

50 mg/day on a Schedule 4/2 for subjects enrolled in Arm C. Sunitinib dose reductions occur in succession based on the previous dose level (37.5, 25 mg/day schedule 4/2).

Dose reduction could be applied to lenvatinib (either 20mg/day or 18mg/day reduce to 14, 10, and 8 mg/day), everolimus (5 mg every day reduce to 5 mg every other day), and sunitinib (50 mg/day reduce to 37.5, 25 mg/day of schedule 4/2). Dose interruption could apply to all study drugs. Definition of dose interruption only includes the scenario that the before and after dose 0 (interruption period), the dose levels or dosing frequency are the same. For example: 20 mg lenvatinib followed by 0 mg and followed by 20 mg lenvatinib; 5 mg everolimus every day followed by 0 mg followed by 5 mg everolimus every day. If dose level reduces from previous dose level after dose interruption period (dose 0), it should count into dose reduction not dose interruption. For example: (1) 20 mg/day lenvatinib followed by 0 mg followed by 14 mg/day lenvatinib; (2) 5 mg everolimus every day followed by 0 mg followed by 5 mg everolimus every other day; the period with 0 mg should not count into dose interruption instead should count as dose reduction. If after dose 0 mg, the subject discontinued from treatment permanently, it should count as treatment discontinuation instead of dose interruption.

Number of subjects with dose reductions and dose interruptions of lenvatinib, everolimus, sunitinib, and pembrolizumab (dose reduction not applied to pembrolizumab) will be summarized by frequency counts and percentages according to study medication data.

Time to first dose reduction is defined as the date of the first dose to the date of first dose reduction, or the date of first dose interruption if subjects had dose interruption followed by dose reduction. There will be two ways to estimate the time to dose reduction. (1) Only include the subjects who had dose reduction events. Descriptive statistics will be generated to describe the time to first dose reduction for these patients. (2) Include all subjects. For subjects who did not have dose reduction, it will be censored at the date of last dose. For this summary, Kaplan-Meier method will be used to estimate the median time to first dose reduction for all the subjects by the treatment arms.

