9.4 Treatments

9.4.1 Treatments Administered

Combination lenvatinib plus everolimus arm (Arm A): Lenvatinib 18 mg QD plus everolimus 5 mg QD will be taken orally in each 21-day cycle.

Combination lenvatinib plus pembrolizumab arm (Arm B): Lenvatinib 20 mg QD will be taken orally in each 21-day cycle. Pembrolizumab will be administered at a dose of 200 mg IV over 30 minutes on Day 1 of each 21-day cycle.

Sunitinib arm (Arm C): Sunitinib 50 mg once daily will be administered orally for 4 weeks on treatment followed by 2 weeks off (Schedule 4/2) in each 21-day cycle.

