9.4.2.11 Management of Hemorrhage

Dose modification guidelines for lenvatinib- (Arm A, Arm B) and sunitinib- (Arm C) related adverse events should be followed for the management of hemorrhage (see [Table 1](#), [Table 2](#), and [Table 5](#)). Either resume study drug at a reduced dose or discontinue lenvatinib/sunitinib, depending on the severity and persistence of hemorrhage.

For subjects receiving treatment with sunitinib (Arm C) who experience hemorrhage associated with thrombocytopenia, treatment interruption is recommended; following resolution, treatment may be resumed at the discretion of the investigator.

9.4.3 Dose Interruption and Dose Reduction for Combination Lenvatinib plus Pembrolizumab Treatment

Lenvatinib

Lenvatinib dose reduction and interruption for subjects who experience lenvatinib pembrolizumab combination therapy-related toxicity will be in accordance with the dose modification guidelines described in [Table 2](#). The investigators will decide the probability of the event being related to 1 or both drugs as to whether dose modification of 1 or both drugs is required.

The starting dose of lenvatinib is 20 mg/day for subjects enrolled in the combination lenvatinib plus pembrolizumab arm. Dose reductions of lenvatinib occur in succession based on the previous dose level (14, 10, and 8 mg/day). Any dose reduction below 8 mg/day must be discussed with the sponsor. Once the study drug dose has been reduced, it may not be increased at a later date, unless the dose was mistakenly decreased; in this situation, the Sponsor's approval is required to increase the dose.

Refer to the following sections for management of hypertension ([Section 9.4.2.1](#)), proteinuria ([Section 9.4.2.2](#)), diarrhea ([Section 9.4.2.3](#)), hepatotoxicity ([Section 9.4.2.7](#)), thromboembolic events ([Section 9.4.2.8](#)), PRES/RPLS ([Section 9.4.2.9](#)), hypocalcemia ([Section 9.4.2.10](#)), and hemorrhage ([Section 9.4.2.11](#)), as appropriate, before consulting dose modification table ([Table 2](#)).

Table 2 Dose Modification Guidelines for Lenvatinib-Related Adverse Events (for the Lenvatinib-Pembrolizumab Combination Arm)

Treatment-Related Toxicity ^{a,b}	Management	Dose Adjustment
Grade 1 or Tolerable Grade 2		
	Continue treatment	No change
Intolerable Grade 2^{c,d} or Grade 3^e		
First occurrence	Interrupt lenvatinib until resolved to Grade 0-1, or tolerable Grade 2	Reduce lenvatinib dose to 14 mg once a day (1-level reduction)

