9.7.1.8.1 EXTENT OF EXPOSURE

The number of cycles/days on treatment, quantity of study drugs administered, and the number of subjects requiring dose reductions, treatment interruption, and treatment discontinuation due to AEs will be summarized.

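### The SAP drops any dose interruption that is followed by a reduction or a permanent stop, so medication-data interruption figures understate toxicity holds of lenvatinib and sunitinib

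*SAP*

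**What the plan says.** SAP Section 5.6.1.3 plans, from the study medication data, the number of subjects with reductions and with interruptions of each drug. It also plans reasons for both, and times to first reduction and first interruption, for lenvatinib, everolimus and sunitinib. The definition is restrictive: "dose interruption only includes the scenario that the before and after dose 0 (interruption period), the dose levels or dosing frequency are the same". Two exclusions follow.

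- Lower dose after the hold: "If dose level reduces from previous dose level after dose interruption period (dose 0), it should count into dose reduction not dose interruption". The worked examples repeat this: "the period with 0 mg should not count into dose interruption instead should count as dose reduction".
- Permanent stop after the hold: "it should count as treatment discontinuation instead of dose interruption".

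Time to first reduction is defined, and is dated from the preceding hold where there was one. Time to first interruption is promised but not defined.

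The protocol's toxicity tables work in two steps. For lenvatinib in Arm B (Section 9.4.3, Table 2) the first step is "Interrupt lenvatinib until resolved to Grade 0-1, or tolerable Grade 2"; the second is a one-level reduction. Table 1 does the same for lenvatinib in Arm A, and Table 5 for sunitinib.

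Protocol Section 9.7.1.8.1 describes the summary without any exclusion based on what happened after the hold: "the number of subjects requiring dose reductions, treatment interruption, and treatment discontinuation due to AEs will be summarized".

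**The concern.** The holds that the SAP leaves out are the ones the protocol prescribes when lenvatinib or sunitinib is not tolerated. What remains for these two drugs is mainly holds outside the toxicity tables, or holds resumed at the same dose. A reader who sees a percentage of subjects with dose interruption will take it as the share of subjects whose drug was ever held. Under this rule it is not.

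Everolimus and pembrolizumab are affected far less. Everolimus is often resumed at its previous dose, and pembrolizumab has no dose reduction. Percentages for the two components of one combination would therefore rest on different effective definitions.

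**Working it through.** The plan gives no figure for interruptions, so there is nothing to reproduce. The check applies the SAP rule literally to the protocol's own dose sequences.

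**Rule.** For each run of level a, 0 mg, level b: if b = a, count an interruption; if b is lower than a, count a reduction only; if nothing follows the 0 mg, count a discontinuation only.

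**Inputs.** Dose levels come from protocol Tables 1, 2 and 5. Resumption of everolimus at the same dose comes from Table 1 (at first occurrence, and for Grade 2 toxicity under footnote e). Resumption of withheld pembrolizumab comes from Table 3. Scheduled sunitinib rest weeks are left out of the sequence here.

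| Drug and sequence (mg) | Holds | Interruptions under SAP | Reductions under SAP | Interruptions if every hold counts |
|---|---|---|---|---|
| Lenvatinib, Arm A: 18-0-14-0-10-0-8 | 3 | 0 | 3 | 3 |
| Lenvatinib, Arm B: 20-0-14-0-10-0-8 | 3 | 0 | 3 | 3 |
| Sunitinib: 50-0-37.5-0-25 | 2 | 0 | 2 | 2 |
| Everolimus, Grade 2 each time: 5-0-5-0-5-0-5 | 3 | 3 | 0 | 3 |
| Pembrolizumab, withheld once: 200-0-200 | 1 | 1 | none defined | 1 |

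**Within Arm A.** The first and fourth rows can describe the same three episodes in one subject, because Table 1 holds both drugs together. The SAP would report three interruptions of everolimus and none of lenvatinib.

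**Time to first interruption.** If the first hold is followed by a reduction, the clock runs on to the first later hold that is resumed at the same dose. If there is none, the subject has no event. Dropping early holds can only move the first counted interruption later or remove it.

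**Internal consistency.** When it defines time to first reduction, the same SAP section describes an interruption followed by a reduction. That is the combination its own definition has just ruled out.

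**Scheduled off-periods.** Protocol Section 9.4.1 gives sunitinib as "4 weeks on treatment followed by 2 weeks off", a 42-day course. The SAP does not say how rest weeks are handled. If they were stored as 0 mg, which is an assumption about the data, the sequence 50-0-50 would match the literal definition. Over the 15 months of treatment estimated in the protocol synopsis, 15 × 30.4375 / 42 = 10.87 courses, so about 10 rest periods would be followed by re-dosing. If they are not stored as 0 mg, the number is 0.

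**The case against.** The case for leaving the rule alone has real substance.

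- **Nothing is lost.** Each excluded hold is counted as a reduction or a discontinuation, and time to first reduction starts from the hold. Percentage of planned dose and dose intensity (SAP Section 5.6.1.2) reflect missed doses. This stands, and it limits the harm, but it does not make the interruption figures mean what their label says.
- **The adverse-event view is planned separately.** SAP Section 5.6.2 has an overview of events leading to dose interruption, and Section 5.6.2.1 tabulates events leading to reduction and/or interruption, overall and by drug. The combined tables capture a hold-then-reduce episode however it is classified. This stands. However, those tables do not separate the two actions, and the overview may give an interruption figure that differs from the medication-data one with no explanation.
- **Hold-then-reduce is not universal.** Everolimus at first occurrence and both Arm A drugs after a first Grade 2 pneumonitis restart at the same dose, as can withheld pembrolizumab. Surgical holds lie outside the toxicity tables. This stands: the point concerns the standard sequence for lenvatinib and sunitinib, not every hold.
- **Lenvatinib and sunitinib are treated alike.** The exclusions are worded identically for both, so a bias between arms is a risk and not an established result. This stands.

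A reader might infer that the SAP counts sunitinib rest weeks as interruptions, so that Arm C approaches 100%. The documents do not support that. The SAP calls the 0 mg span an interruption period and writes sunitinib dose levels with the 4/2 schedule attached. The same literal reading would also turn the gaps between pembrolizumab infusions and everolimus every-other-day off-days into interruptions, which is clearly not meant. Derivation rules sit in separate specifications (SAP Section 9) that are not among these documents. This is a missing exclusion sentence and no more.

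**Conclusion.** The point holds as a matter of reporting, and it is minor. For a subject managed by the protocol tables, 3 of 3 lenvatinib holds or 2 of 2 sunitinib holds go uncounted as interruptions. The number of subjects affected cannot be derived, because the documents give no frequencies. It ranges from none, if every subject with such a hold also had one resumed at the same dose, to all subjects whose only holds led to a reduction or a stop. Time to first interruption is biased towards late or missing values. Per-drug percentages within Arms A and B are not comparable, and the count is narrower than the one in protocol Section 9.7.1.8.1.

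It would be tempting to conclude that the trial's tolerability comparison is wrong. The documents do not support that either. The tolerability objective names discontinuation due to toxicity and time to treatment failure due to toxicity, and neither uses this count. The interruption figures are descriptive and untested, and no primary or key secondary analysis depends on them.

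The conclusion assumes that the dataset specifications follow the SAP text as written and that sites follow Tables 1, 2 and 5.

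**What to change.** In SAP Section 5.6.1.3 and the dataset specifications:

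1. Count a subject as having an interruption of a drug if there is any unplanned 0 mg period, whatever follows.
2. Report beneath it three subcategories that need not be mutually exclusive: resumed at the same dose, resumed at a reduced dose, not resumed. The present categories can be kept alongside.
3. Define time to first interruption from the first dose to the start of the first such period.
4. As a clarification only, state that protocol-scheduled off-periods are not interruptions: Schedule 4/2 rest weeks, the gaps between pembrolizumab infusions, and the off-days of everolimus every other day.

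The cost is a wording and programming change on data already collected. Interruption counts will rise and will overlap with reductions and discontinuations, so the tables need a footnote saying that categories do not add up. Patient management is unchanged.

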- For minor procedures: stop lenvatinib at least 2 days before the procedure and restart it at least 2 days after, once there is evidence of adequate healing and no risk of bleeding.
- For major procedures: stop lenvatinib at least 1 week (5 half-lives) prior to surgery and then restart it at least 1 week after, once there is evidence of adequate healing and no risk of bleeding.

Any additional procedural or patient specific particularities should be discussed with the sponsor.

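### The SAP's date for the first dose reduction is not tied to the hold that leads into it, so an earlier hold resumed at the same dose can be taken as the reduction date

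*SAP*

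**What the plan says.** All the relevant SAP text is in Section 5.6.1.3.

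- **Reduction.** "Dose reduction refers to the situation that a dose level was reduced from the previous dose level without going back".
- **Interruption.** The definition "only includes the scenario that the before and after dose 0 (interruption period), the dose levels or dosing frequency are the same".
- **Hold that ends in a lower dose.** "If dose level reduces from previous dose level after dose interruption period (dose 0), it should count into dose reduction not dose interruption". For the two worked examples of this pattern, "the period with 0 mg should not count into dose interruption instead should count as dose reduction".
- **Date of the first reduction.** Time runs from the first dose to the first reduction, "or the date of first dose interruption if subjects had dose interruption followed by dose reduction".
- **Use.** The time is summarised descriptively among subjects with a reduction. In addition, "Kaplan-Meier method will be used to estimate the median time to first dose reduction for all the subjects by the treatment arms". Subjects without a reduction are censored at the last dose.

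The section lists time to first reduction and time to first interruption as separate summaries for lenvatinib, everolimus and sunitinib.

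**The concern.** The clause evidently aims to date a reduction at the start of the hold that produced it. As worded, it differs from that aim in two ways.

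First, it relies on the word interruption, which the section has just restricted to holds resumed at the same dose. In that strict sense it can only select holds that did not themselves end in a reduction.

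Second, it asks for the first interruption and does not require it to be next to the reduction. An interruption months before, with full dosing resumed in between, satisfies the wording.

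A programmer who follows the sentence would report some reductions too early. For those subjects, time to first reduction and time to first interruption would fall on the same date, although the SAP plans them as two separate summaries. The more same-dose holds an arm has, the more its reduction times would reflect interruptions.

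**Working it through.** The SAP gives no figure to reproduce, so the rule is applied to dosing histories and then to a simple model.

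**1. Constructed lenvatinib histories.** The days are assumed, with first dose on Day 1. Time is the event day minus 1, divided by 30.4375 (SAP 8.2.2) for months.

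| History | Clause, strict sense of interruption | Start of the hold leading into the reduction | First lower dose |
|---|---|---|---|
| (a) 20, 0 from Day 30, 14 from Day 44 | clause does not apply | 29 days (0.95 months) | 43 days (1.41) |
| (b) 20, 0 from Day 30, 20 from Day 37, 0 from Day 120, 14 from Day 134 | 29 days (0.95) | 119 days (3.91) | 133 days (4.37) |
| (c) 20, 0 from Day 30, 20 from Day 37, 14 from Day 120 | 29 days (0.95) | no such hold | 119 days (3.91) |

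In (b) and (c) the reduction is dated 119 − 29 = 90 days early.

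**2. The same histories with interruption meaning any 0 mg period.** In (a) the clause now gives Day 30, the start of the right hold. In (b) the first interruption is still Day 30. In (c) an interruption is still followed, later, by a reduction, so the date is again Day 30. The looser sense repairs (a) only.

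**3. Does the protocol produce history (b)?** Yes, most directly for everolimus. In Protocol Table 1 the first occurrence of intolerable Grade 2 or Grade 3 toxicity interrupts both drugs, and everolimus is resumed at its previous dose. An everolimus reduction may be considered only from the second occurrence. A subject who reaches an everolimus reduction along this table therefore already has a same-dose everolimus hold, and the clause picks that hold.

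For lenvatinib, same-dose holds can arise in at least two ways:
- Protocol 9.4.2.4 lets Arm A restart at the same doses after Grade 2 non-infectious pneumonitis.
- Protocol 9.4.10 tells sites, for minor procedures, to "stop lenvatinib at least 2 days before the procedure and restart it at least 2 days after".

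**4. Possible size.** The documents give no rates of same-dose interruption or of first reduction, so the rates here are assumptions. Let first reductions occur at rate r per month, same-dose interruptions at rate i, and treatment end at rate 1/15, all exponential and independent. The 15 months is the treatment duration estimated in the protocol synopsis. Among subjects with a reduction:

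- share dated too early = i / (i + r + 1/15)
- mean shift in those subjects = 1 / (r + 1/15) months
- median time = ln 2 / (r + 1/15) with the correct date, and ln 2 / (i + r + 1/15) under the clause

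| r | i | Share too early | Mean shift (months) | Median: correct → clause (months) |
|---|---|---|---|---|
| 0.30 | 0.05 | 0.05/0.417 = 12% | 2.7 | 1.9 → 1.7 |
| 0.20 | 0.05 | 0.05/0.317 = 16% | 3.7 | 2.6 → 2.2 |
| 0.10 | 0.03 | 0.03/0.197 = 15% | 6.0 | 4.2 → 3.5 |
| 0.05 | 0.05 | 0.05/0.167 = 30% | 8.6 | 5.9 → 4.2 |
| 0.10 | 0.10 | 0.10/0.267 = 38% | 6.0 | 4.2 → 2.6 |
| 0.05 | 0.20 | 0.20/0.317 = 63% | 8.6 | 5.9 → 2.2 |

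Simulation with 400,000 subjects per setting agrees. Capping treatment at 40 months lowers the 8.6-month shift to about 8. In the same simulation the Kaplan-Meier median over all subjects moves from about 13.9 to 11.6 months at r = i = 0.05, and from about 6.9 to 4.8 months at r = i = 0.10.

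**The case against.** The case for leaving the text alone has four parts.

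**The benign reading.** The section itself calls the hold before a lower dose an interruption period. Protocol Tables 1, 2 and 5 prescribe hold-then-reduce for lenvatinib and sunitinib from the first occurrence of toxicity. On that view the clause just means the start of the hold that ends in the reduction. This is very probably the intent, and it gives a sensible date in history (a). It does not rescue (b): even if followed by is read as directly followed by, the condition is met, and the date then supplied is still that of the first interruption.

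**The derivation may be settled elsewhere.** SAP Section 9 places derivation rules in separate documents, which are not available here. They may already be right. They should nevertheless implement the SAP, so the SAP should state the rule.

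**The sizes are assumed.** This stands. The nearest figure in the protocol (Section 7.1.4) is that 28 of 30 RCC subjects (93%) in the earlier lenvatinib-pembrolizumab study had a dose adjustment for an adverse event. It is not split into reductions and interruptions. If reductions come early, the shares and shifts lie at the low end of the table, and the 63% needs same-dose interruptions four times as frequent as reductions.

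**Little depends on it.** This also stands. No between-arm test is planned for this summary. The counts of reductions and interruptions do not use the date. The SAP separately plans time to first interruption, time to treatment failure due to toxicity, and time to onset of adverse events of clinical interest.

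**Conclusion.** The point holds as a minor defect in a stated rule. For any subject with a same-dose hold before the first reduction, the clause as worded returns the earlier hold, whichever sense of interruption is used. The direction is always earlier and needs no assumption. The size is unknown. Under the assumed rates above, 12% to 63% of subjects with a reduction would be dated too early, by about 3 to 9 months on average; these figures illustrate and do not predict.

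Three stronger conclusions might be inferred, and the documents do not support them:

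- **That every reduction is dated at an interruption.** The default is the date of the reduction, and the clause is conditional. Subjects with no earlier same-dose hold are not moved to an earlier hold.
- **That the earlier hold is always unrelated to the reduction.** It may concern the same toxicity. Under the SAP's definitions it is still not a reduction.
- **That the arms are known to be affected unequally.** This is possible, but the documents give no interruption rates by arm.

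Only the descriptive and Kaplan-Meier summaries of time to first reduction are affected. No efficacy endpoint, test, alpha or power calculation is.

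**What to change.** In SAP 5.6.1.3, replace the clause after the comma with: or, if the reduction directly follows a 0 mg period, the first day of that 0 mg period; earlier interruptions resumed at the same dose are ignored.

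Apply the rule to both the descriptive and the Kaplan-Meier summary, and carry it into the dataset specification. History (b) above is a useful test case: the derivation should return 119 days. In history (c), where no hold directly precedes the reduction, it should also return 119 days, the date of the lower dose itself.

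The cost is one sentence in the SAP and a check of the matching derivation. No new data are needed.

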Dose modification guidelines for lenvatinib- (Arms A and B) and sunitinib- (Arm C) related adverse events should be followed for the management of hemorrhage. Either resume lenvatinib/sunitinib at a reduced dose or discontinue lenvatinib/sunitinib, depending on the severity and persistence of hemorrhage.

For subjects receiving treatment with sunitinib (Arm C) who experience hemorrhage associated with thrombocytopenia, treatment interruption is recommended; following resolution, treatment may be resumed at the discretion of the investigator.

Duration of Treatment

A subject will remain on study treatment until 1 or more of the following events occur(s):

- Progressive Disease (PD) (as confirmed by independent review)
Note: Subjects will be permitted to continue treatment beyond initial RECIST 1.1-defined progression as long as investigator-assessed clinical benefit is observed and the subject is tolerating study drug. Subjects will discontinue study treatment upon evidence of further progression and/or loss of clinical benefit as judged by the Investigator.
- Unacceptable toxicity
- Subject request
- Withdrawal of consent
- Completion of 35 treatments (approximately 2 years) with pembrolizumab
- Termination of the study by the Sponsor

The duration of treatment for each subject is estimated to be approximately 15 months.

Concomitant Drug/Therapy

Treatment (including blood products, blood transfusions, fluid transfusions, antibiotics, and antidiarrheal drugs, etc.) of complications of AEs or therapy to ameliorate symptoms may be administered at the discretion of the investigator, unless it is expected to interfere with the evaluation of (or to interact with) the study medication.

The following concomitant therapies are also **allowed**:

- Thyroid hormone suppressive therapy
- Adjuvant hormonal therapy for history of definitively treated breast or prostate cancer
- Anticoagulants including low molecular weight heparin (LMWH), warfarin, anti-Xa agents
- Antiinflammatory agents
- Bisphosphonates or denosumab
- Antihypertensive therapy (including additional antihypertensive treatment as appropriate if BP increases once the subject is enrolled)
- Palliative radiotherapy of up to 2 painful pre-existing, non-target bone metastases will be permitted without being considered PD

If the subject is receiving treatment with lenvatinib and requires surgery during the study, the stop time and restart time of lenvatinib should be as follows:

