## 4 DETERMINATION OF SAMPLE SIZE

The sample size is estimated based on the primary endpoint PFS. Approximately 1050 subjects will be randomized in a 1:1:1 ratio into one of the three treatment arms: lenvatinib + everolimus, lenvatinib + pembrolizumab, or sunitinib alone. The randomization scheme will be stratified by geographic region (Western Europe and North America versus Other) and MSKCC prognostic groups (favorable, intermediate and poor risk).

The same treatment effect is assumed for the primary comparisons of lenvatinib + everolimus (Arm A) and lenvatinib + pembrolizumab (Arm B) each compared to sunitinib alone (Arm C). Assuming the median PFS in sunitinib alone (Arm C) to be 12.3 months and a hazard ratio of 0.714 for the primary comparisons, this corresponds to 40% improvement (4.9 months) in median PFS from 12.3 months to 17.2 months for Arm A versus Arm C and for Arm B versus Arm C. A yearly loss of PFS event rate of 22% is assumed in the sample size calculation. Since the study is testing more than one comparison for the primary and secondary endpoints, the graphical approach (SAP [Section 5.3.3](#)) will be used for testing multiple hypotheses. For the two PFS comparisons (one for each test arm), the sponsor chooses to split the total alpha of 0.0499 (2-sided), as initial allocations, into  $\alpha = 0.045$  for the comparison between Arm B and Arm C, and  $\alpha = 0.0049$  for the comparison between Arm A and Arm C.

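### The all-subject Kaplan-Meier median time to first dose reduction censors permanent discontinuation, so it falls at or before the time by which half of treated subjects are actually reduced

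*SAP*

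**What the plan says.** SAP 5.6.1.3 summarises time to first dose reduction for lenvatinib, everolimus and sunitinib. The clock is set as follows: "Time to first dose reduction is defined as the date of the first dose to the date of first dose reduction", or to the start of an interruption that leads into a reduction. Two estimates are planned.

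- The first is descriptive: "Only include the subjects who had dose reduction events".
- The second takes in everyone. Its censoring rule is "For subjects who did not have dose reduction, it will be censored at the date of last dose", and its output is "Kaplan-Meier method will be used to estimate the median time to first dose reduction for all the subjects by the treatment arms".

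Three other provisions bear on this.

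- SAP 5.6.1.1 sets the dosing end date to the cutoff for subjects still on treatment.
- SAP 5.6.1.3 treats a permanent stop as an outcome of its own: "If after dose 0 mg, the subject discontinued from treatment permanently, it should count as treatment discontinuation instead of dose interruption".
- The number of subjects with reductions is reported separately and "will be summarized by frequency counts and percentages according to study medication data".

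Neither document plans a competing-risk estimate here or says that the median refers to a setting in which nobody stops.

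**The concern.** The censoring rule puts two different groups together. A subject still on drug at the cutoff may yet be reduced, and censoring is right. A subject who has stopped for progression, toxicity, withdrawal or death cannot be reduced later. Kaplan-Meier assumes that such a subject would have gone on to be reduced at the same rate as those who stayed on drug.

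The output is labelled as covering all subjects, so a reader will take the median as the time by which half of the treated subjects had a reduction. It is not that time.

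Comparing tolerability with sunitinib is a secondary objective (SAP 3.1.2), and this is the only planned all-subject estimate of when reductions occur. The reducers-only summary conditions on having had the event, and the counts carry no timing, so neither fills the gap.

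**Working it through.** **Plan's own figure.** The documents state no time to dose reduction and no reduction rate, so there is nothing to reproduce. The PFS inputs used below are consistent with each other: 12.3 / 0.714 = 17.23, against the stated 17.2 months.

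**Direction, with no rates assumed.** At each reduction time, 1 − KM grows by S_KM × (reductions / number at risk). The cumulative incidence grows by S_all × (reductions / number at risk). S_KM drops only at reductions, while S_all drops at reductions and at permanent stops, so S_KM ≥ S_all throughout. Hence 1 − KM is never below the cumulative incidence, and the Kaplan-Meier median is never later than the time at which the cumulative incidence reaches 50%.

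**Inputs for the size.**
- Reduction hazard r = ln 2 / m, where m is the Kaplan-Meier median. This is an assumption, varied from 2 to 24 months and set equal in all arms.
- Stop hazard d = ln 2 / s, with s = 12.3 months (Arm C) or 17.2 months (Arms A and B), from SAP section 4: "median PFS from 12.3 months to 17.2 months for Arm A versus Arm C and for Arm B versus Arm C". This is a proxy; PFS is not a discontinuation rate.
- Alternative stop hazard d = 1/15 per month for all arms, reading the Protocol synopsis figure as a mean: "The duration of treatment for each subject is estimated to be approximately 15 months".

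**Formulas, constant hazards.**
- Long-run proportion ever reduced: L = r / (r + d) = s / (m + s).
- Cumulative incidence: CIF(t) = L × [1 − exp(−(r + d)t)].
- Time to 50%: t = −ln(1 − 0.5/L) / (r + d), which exists only if L > 0.5.

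**Example, m = 6, s = 12.3.** L = 12.3/18.3 = 0.672. r + d = 0.6931 × (1/6 + 1/12.3) = 0.1719. Then t = −ln(1 − 0.5/0.672) / 0.1719 = 7.93 months, against a reported median of 6.

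| KM median m (months) | Arm C: ever reduced | Arm C: time to 50% (months) | Arms A, B: ever reduced | Arms A, B: time to 50% (months) |
|---|---|---|---|---|
| 2 | 86.0% | 2.16 | 89.6% | 2.11 |
| 4 | 75.5% | 4.73 | 81.1% | 4.48 |
| 6 | 67.2% | 7.93 | 74.1% | 7.20 |
| 9 | 57.7% | 15.1 | 65.6% | 12.2 |
| 12 | 50.6% | 38.6 | 58.9% | 19.3 |
| 24 | 33.9% | not reached | 41.7% | not reached |

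**Alternative stop rate.** With d = 1/15, Kaplan-Meier medians of 2 and 6 months correspond to 2.19 and 8.53 months. At 12 months, 46.4% are ever reduced and 50% is not reached.

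**A finite median with fewer than half reduced.** Take d = 1/15 = 0.0667 and r = 0.0444. Then L = 0.0444 / 0.1111 = 40%, yet the Kaplan-Meier median is 0.6931 / 0.0444 = 15.6 months.

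**Check by simulation.** Runs of 200,000 subjects with 34 months' accrual and a 45-month cutoff agree. For m = 8, Kaplan-Meier gives 8.0 months with either stop rate, while the cumulative incidence reaches 50% at 12.3 months (Arm C) and 10.4 months (Arms A and B). For m = 12, the corresponding times are 37.0 and 19.3 months. The Arm C value is imprecise because the incidence is nearly flat there.

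**The case against.** The strongest defence is that Kaplan-Meier answers a legitimate question: how soon reductions occur among subjects who remain on drug. With equal reduction hazards, as in the table, it returns the same median in every arm, whereas the cumulative incidence is lower in the arm that stops sooner. An arm could then look better tolerated only because its subjects progress earlier.

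Part of this stands. The two estimates answer different questions, and a cumulative incidence has to be read beside the incidence of stopping. But the SAP does not state the while-on-treatment target, and that reading needs stops to be independent of reduction risk. Protocol Tables 1, 2 and 5 make this doubtful: intolerable Grade 2 or Grade 3 toxicity leads to reduction and Grade 4, with a laboratory exception, to discontinuation. Both outcomes come from the same toxicity process.

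A second objection is that the shift may be trivial. Protocol 7.1.4 reports a dose adjustment for an adverse event in 28 of 30 subjects with RCC (93%) on lenvatinib plus pembrolizumab. That count includes interruptions, so it is not a reduction rate, but early and frequent reductions are plausible, and the median would then move little. This stands as a limit on size.

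Two stronger readings are tempting, and the documents do not support either.

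- A reader might infer that the plan will overstate how many subjects are reduced. It will not: the only Kaplan-Meier output named is the median, no curve or 12-month proportion is planned, and the counts and percentages do not depend on the censoring rule.
- A reader might infer that the plan's own assumptions make the error differ between arms. It may differ if the arms stop at different rates, but no discontinuation rates are stated. PFS is only a proxy, because treatment may continue past progression or end earlier for toxicity. The one treatment-duration figure is common to all arms, and Arms A and B share one assumed PFS.

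**Conclusion.** The point holds for the all-subject median. Its direction is an algebraic property of the two estimators and needs no assumed rates. Its size cannot be fixed from the documents. With constant hazards and planned median PFS standing in for time to stopping, it runs from 0.1 to 0.2 month at a Kaplan-Meier median of 2 months, through 1.2 to 1.9 months at 6, to about 7 to 27 months at 12. At 24 months the cumulative incidence never reaches 50%.

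The consequence is small. The summary is descriptive with no test attached, type I error is not involved, and the reported counts of reduced subjects, PFS, OS and ORR stay as they are. It is worth correcting because the label promises something that the estimate does not deliver.

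**What to change.** In SAP 5.6.1.3, for each drug that can be reduced, replace the all-subject Kaplan-Meier estimate with the Aalen-Johansen cumulative incidence of first dose reduction, by arm, with 95% CI. Count permanent discontinuation of that drug without a prior reduction, for any reason including death, as the competing event. Censor only subjects still on that drug at the data cutoff. Give a median only if the cumulative incidence reaches 50%. Showing the incidence of the competing event in the same table would let the two be read together.

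State that last dose means the last dose of the drug in question. SAP 5.3.6 defines end of treatment in Arms A and B as the later of the two drugs' last doses, and 5.6.1.3 does not say which applies.

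If the Kaplan-Meier median is kept alongside, label it as conditional on remaining on treatment.

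The cost is one paragraph of SAP text and one added or changed table, from dosing and discontinuation dates already collected.
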